1 GENERAL INFORMATION

1.1 Introduction

Truncal acne is an under diagnosed and under treated condition. Aczone gel 7.5% has already been approved for the treatment of acne vulgaris. However, topical treatment of truncal acne is very difficult in traditional vehicles due to the difficulty of covering large body surface areas. The recent approval of Aczone gel 7.5% foam gives us an opportunity to address this unmet need. Therefore, the current pilot study will investigate the efficacy and safety of Aczone 7.5% gel in the treatment of truncal acne.

Truncal acne is estimated to occur in 61 percent and 45 percent of acne patients, respectively. 1.2 The pathophysiology of truncal acne is the same as facial acne, and both respond similarly to therapy. However, despite a wide range of treatment options available, the management of truncal acne remains challenging. Clinicians tend to emphasize oral therapies over topical interventions for truncal acne as it is typically assumed oral medications are more convenient than applying topical applications to large and potentially hard-to reach body areas. This line of reason is based on using standard creams or gels and does not necessarily hold-up with the advent of foam formulations that are significantly more convenient in treating hard-to-reach areas and larger surface areas. In fact, foam vehicles are associated with improved usability, better adherence and, consequently, improved therapeutic results. 5,6,7,8,9,10,11,12 Aczone gel 7.5% has been approved by the FDA for the treatment of acne vulgaris in individuals who are older than 12 years of age. Aczone gel 7.5% have been used on the chest and back acne during the phase III clinical trials but its efficacy has not been an endpoint in this study. It is reasonable to assume that Aczone gel 7.5% could present to be a viable treatment option for truncal acne. The current pilot study will investigate the efficacy and safety of Aczone gel 7.5% in the treatment of truncal acne. Based on the recent phase III clinical study of aczone gel 7.5%, it is expected that the typical risk/benefit profile of aczone gel 7.5% should apply in the treatment of truncal acne (ie, reduction in acne signs and symptoms, with possible adverse effects such as burning, stinging, tingling, pruritus, dry skin, erythema and/or edema).

- 1. Thomas DR. Psychosocial effects of acne. J Cutan Med Surg. 2004;8 Suppl 4:3-5.

1.2 Study Population

Thirty (30) subjects with acne vulgaris with moderate truncal acne.

2 STUDY OBJECTIVES

The objectives of this study are to observe the efficacy and safety of Aczone gel 7.5% as a treatment modality for moderate truncal acne.

3 STUDY DESIGN

This is a three-center, open-label pilot study ([name] Louisville, KY, [name], DO, Las Vegas, NV & [name] Sacramento, CA.). All study subjects will receive Aczone gel 7.5% at Visit 1. The duration of the study is 16 weeks and consists of a Screening, Baseline Visit, and three (3) Follow-up Visits at Weeks 4, 10, and 16.

4 SELECTION AND WITHDRAWAL OF SUBJECTS

4.1 Inclusion Criteria

i. Outpatient, male or female subjects of any race, and at least 12 years of age. Female subjects of childbearing potential must have a negative urine pregnancy test result at Baseline (test must have a sensitivity of at least 25mlU/ml for human chorionic gonadotropin) and practice a reliable method of contraception throughout the study:

A female is considered of childbearing potential unless she is:

- postmenopausal for at least 12 months prior to study drug administration;
- without a uterus and/or both ovaries; or
- has been surgically sterile for at least 6 months prior to study drug administration.

Reliable methods of contraception are:

- hormonal methods or intrauterine device in use ≥ 90 days prior to study drug administration;
- barrier methods plus spermicide in use at least 14 days prior to study drug administration; or
- vasectomized partner (vasectomy must be performed 3 months prior to first study drug administration or in the alternative a zero sperm count will suffice)

[Exception: Female subjects of childbearing potential who are not sexually active will not be required to practice a reliable method of contraception. These subjects may be enrolled at the Investigator's discretion if they are counseled to remain sexually inactive during the study and understand the possible risks in getting pregnant during the study.]

- ii. Truncal acne IGA score of 3.
- iii. Able to understand the requirements of the study and sign Informed Consent/HIPAA Authorization forms. Subjects under the legal age of consent in the state where the study is conducted must also have the written, informed consent of a parent or legal guardian.

4.2 Exclusion Criteria

المنافعة الم

- i. Female subjects who are pregnant (positive urine pregnancy test), breast-feeding, or who are of childbearing potential and not practicing a reliable method of birth control.
- ii. Allergy or sensitivity to any component of the test medication (Section 5.2).
- iii. Subjects who have not complied with the proper wash-out periods for prohibited medications (Supplement I).
- iv. Medical condition that, in the opinion of the Investigator, contraindicates the subject's participation in the clinical study.
- v. Skin disease/disorder that might interfere with the diagnosis or evaluation of acne vulgaris
- vi. Evidence of recent alcohol or drug abuse.
- vii. History of poor cooperation, non-compliance with medical treatment, or unreliability.
- viii. Exposure to an investigational drug study within 30 days of the Baseline Visit.

4.3 Withdrawal of Subjects

It is the right and duty of the Investigator to discontinue the study participation of a subject when the subject's health or well-being is threatened by continuation in the study. Such subjects should be withdrawn from the study.

The following are circumstances that would result in the subject's discontinuation from the study:

- the subject experiences a serious adverse event rendering them unable to continue study participation;
- the subject is unable to physically or mentally tolerate the use of the test medication:
- an exclusion criterion becomes apparent at any time during the study; or
- the subject voluntarily withdraws.

In the event of premature discontinuation from the study, the Investigator should determine the primary reason for discontinuation. A subject who is withdrawn from the study prior to initiation of treatment may be replaced.

TREATMENT OF SUBJECTS AND FOLLOW-UP 5

5.1 **Study Procedures**

5.1.1 Assessment Schedule

		Screening/ Baseline	Follows	up Visits
		Visit 1 Wk 0	Visit 2, 3 Wk 4, 10	Visit 4 Wk 16
ICI	F/HIPAA	Х		
	bject Demographics/Medical /Height	х		
W	eight	X		X
Inc	clusion/Exclusion Criteria	Х		
Ph	ysical Exam	Х		
Vit	al Signs	X	Χ	X
Uri	ne Pregnancy Test	X ¹	X ¹	X ¹
Assessments	Truncal Acne IGA Truncal Lesion Counts ² Tolerability ³	x	х	x
Stu	ady Medication; Dispense Collect	D	C D	c
	tient preference questionnaire	, , , , , , , , , , , , , , , , , , ,		X
	ncomitant medication/Treatment	X	X	X
Ad	verse Events		X	Χ.

¹ Female subjects of childbearing potential.

5.1.2 Visit 1 (Screening / Baseline Visit)

- Informed Consent/HIPAA
- Urine Pregnancy Test (if applicable)
- Subject Demographics/Medical History/Height
- Weight
- Vital Signs
- Concomitant Medication/Treatment
- Assessments
 - Truncal Acne IGA
 - Truncal Lesion Counts
 - **Tolerability**
- Inclusion/Exclusion Criteria
- Dispense study medication and instruct regarding application procedures

Lesion Counts: papules, pustules, nodules, open/closed comedones
 Peeling, erythema, dryness, oiliness, burning, pruritus

5.1.3 Visits 2, 3, (Weeks 4, & 10 ± 3 days)

- Concomitant Medication/Treatment
- Urine Pregnancy Test (if applicable)
- Adverse Events
- Vital Signs
- Assessments
 - Truncal Acne IGA
 - Truncal Lesion Counts
 - Tolerability

5.1.4 Visit 4 (Week 16; ± 5 days)

- Urine Pregnancy Test (if applicable)
- Concomitant Medication/Treatment
- Adverse Events
- Vital Signs
- Weight
- Assessments
 - Trunçal Acne IGA
 - Truncal Lesion Counts
 - Tolerability
- Collect Study Medication
- Patient preference questionnaire

5.2 Study Treatment

5.2.1 Details of Study Treatment

ACZONE (dapsone) Gel, 7.5%, contains dapsone, a sulfone, in an aqueous gel base for topical dermatologic use. ACZONE Gel, 7.5% is an off-white to yellow gel with suspended particles. Chemically, dapsone has an empirical formula of C₁₂H₁₂N₂O₂S. It is a white or slightly yellow-white, crystalline powder that has a molecular weight of 248.30. Each gram of ACZONE Gel, 7.5%, contains 75 mg of dapsone, USP, in a gel of diethylene glycol monoethyl ether, methylparaben, acrylamide/sodium acryloyldimethyl taurate copolymer, isohexadecane, polysorbate 80, and purified water.

5.2.2 Storage and Handling

Store at 20°C-25°C (68°F-77°F), excursions permitted to 15°C-30°C (59°F-86°F) [see USP Controlled Room Temperature]. Protect from freezing.

5.2.3 Dispensation and Dosage Schedule

ACZONE Gel is an off-white to yellow gel with suspended particles. It is supplied in an airless pump containing a polypropylene bottle with a high density polyethylene piston. ACZONE (dapsone) Gel, 7.5%, is supplied in 90 gram pump (NDC 0023-5206-90)

After the skin is gently washed and patted dry, apply approximately a pea-sized amount of ACZONE Gel, 7.5%, in a thin layer to the entire affected areas on the trunk once daily. Rub in ACZONE Gel, 7.5%, gently and completely.

ACZ1601 (01JUN2016) Page 7 of 14

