10 SUPPLEMENTS

I Prohibited Medications / Wash-Out Periods

SUPPLEMENT I Prohibited Medications / Wash-Out Periods

Use of the following medications (concurrent and contraindicated treatments) are prohibited during the course of the study and appropriate wash-out periods must be respected:

100 C	Medication	Washout
Topical	Retinoids, antibiotics, BPO, dapsone, bleaching agents	2Weeks washout prior to V1
ОТ	C acne medications or bleaching agents	1Week washout prior to V1

Oral Antibiotics for acne	4Weeks washout prior to V1
Oral Retinoids	24Weeks washout prior to V1
Cryotherapy, chemical peels, microdermabrasion	2Weeks washout prior to V1
Laser Resurfacing and dermabrasion	24Weeks washout prior to V1
Investigational Drugs	4Weeks washout prior to V1

ACZ1601 (01JUN2016) Page 13 of 14

SUPPLEMENT II

Patient's Preference Questionnaire

The aim of this questionnaire is to find out what you like and what you don't like about different types of skin medications that you have used.

1. For all skin medicines you have used in the past, please rate the following treatments in the order you preferred them:

(1= "liked the best", 2= "second best", 3= "third best", 4= "fourth best, 5= "liked the least". If you have not used a certain type of skin medicine, please enter N/A for does not apply to me.)

Gel Lotion Cream Ointment Spr	ray
-------------------------------	-----

2. Please rate the following qualities of the gel, compared to the other skin medicines you have used in the past

(If you have not had a previous experience with other skin medicines, please circle N/A for does not apply to me.)

	Very Inferior "Much Worse"	Inferior "Worse"	About the same	Better	Superior "Much Better"	Does Not Apply to Me
Gel is easy to use	1	2	3	4	5	N/A
I am able to continue daily activities right away following putting the medicine on my skin (i.e., getting dressed, doing school work, playing etc.)	1	2	3	4	5	N/A
The gel leaves my skin feeling soft	1	2	3	4	5	N/A
I am able to apply the gel to large body surface areas	1	2	3	4	5	N/A
The gel disappears into my skin quickly when I apply it	1	2	3	4	5	N/A

3. Please rate the gel on each of the following:

	Very Poor	Poor	Fair	Good	Excellent	Does Not Apply to Me
Moisturizing ("It leaves my skin feeling soft and smooth")	1	2	3	4	5	N/A
Lack of residue ("There is nothing left on my skin")	1	2	3	4	5	N/A
Does not feel greasy	1	2	3	4	5	N/A
Absorbs quickly ("Disappears into my skin quickly after I put it on my skin")	1	2	3	4	5	N/A

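### The amount to apply in Section 5.2.3 is not tied to affected area or a measurable unit, so coverage and exposure may vary between subjects in ways the planned data do not describe

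*Combined protocol and SAP*

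**What the plan says.** Section 5.2.3 asks each subject, once the skin is washed and dry, to "apply approximately a pea-sized amount of ACZONE Gel, 7.5%, in a thin layer to the entire affected areas on the trunk once daily". One sentence therefore sets both an approximate amount and a coverage requirement. It does not say whether the amount applies to each affected area or to the trunk as a whole, and it gives no weight, number of pump strokes or amount per unit area. Section 5.2.1 gives the strength: "Each gram of ACZONE Gel, 7.5%, contains 75 mg of dapsone".

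Elsewhere the protocol treats the trunk as a large surface. Section 1.1 says that "topical treatment of truncal acne is very difficult in traditional vehicles due to the difficulty of covering large body surface areas". The questionnaire in Supplement II has subjects rate the statement "I am able to apply the gel to large body surface areas".

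Four other sections bear on how much gel reaches the skin:

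- Section 4.1 requires a truncal IGA of 3. It sets no limit on affected area and does not ask for it to be recorded.
- Section 5.1.2 has subjects instructed on application at Visit 1, without giving the wording.
- Section 5.2.7 measures compliance by asking about missed applications only.
- Section 5.2.6 requires per-subject records of what was dispensed and returned, but mentions no weighing. Section 8.2 names no summary of amount used.

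**The concern.** For a subject with extensive chest and back acne, the two parts of the instruction may pull apart. Keeping to the amount may leave affected skin untreated. Covering all affected skin may take more than the amount stated. The protocol does not say which part governs.

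This bears on efficacy because the IGA and the lesion counts are truncal and are not restricted to treated skin. Subjects enter at grade 3, and success under Section 6.1 means falling two grades to clear or almost clear. Grade 1 tolerates at most a single small inflammatory lesion. A few inflammatory lesions on skin that the gel never reached could therefore make a subject a non-responder. With no control arm, a low response rate would not show whether the drug failed or was not spread over the lesions.

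It bears on safety because subjects who use enough gel to cover the area will receive different total daily amounts of dapsone. Tolerability scores and adverse events would be summarised over exposures that the planned data do not describe.

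**Working it through.** The protocol states no gram amount and no area, so there is no figure to reproduce. The check asks what follows from the text alone, and then what range the effect could span under stated assumptions.

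**From the documents.** Section 3 states that "The duration of the study is 16 weeks", and application is once daily, so there are 16 × 7 = 112 applications. The strength is 75 mg dapsone per gram.

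**What holds without any assumption about size.** If the amount per application is constant, gel per cm² = amount ÷ area, which falls in proportion to area. If the layer is constant instead, total daily amount = layer × area, which rises in proportion to area. Affected area is not fixed by eligibility, so one or the other varies between subjects unless their affected areas happen to be alike.

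**Assumptions (none is in the documents).** A pea-sized amount weighs 0.25 to 0.5 g, with 1.0 g as an upper check. Affected area is 250 to 5,000 cm². Half a gram spreads over about 300 cm².

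*Gel per unit area, literal reading:*

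- 0.5 g: 500 mg ÷ 250 cm² = 2.0 mg/cm², down to 500 ÷ 5,000 = 0.10 mg/cm²
- 0.25 g: 250 ÷ 250 = 1.0 mg/cm², down to 250 ÷ 5,000 = 0.05 mg/cm²
- Ratio in each case: 5,000 ÷ 250 = 20-fold

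Under the coverage reading with a constant layer, total daily amount varies by the same 20-fold ratio.

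*Share of affected skin covered* = (amount × 300 ÷ 0.5) ÷ area, capped at 100%. The three amounts cover 150, 300 and 600 cm²:

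| Affected area (cm²) | 0.25 g | 0.5 g | 1.0 g |
|---|---|---|---|
| 250 | 60% | 100% | 100% |
| 500 | 30% | 60% | 100% |
| 1,000 | 15% | 30% | 60% |
| 2,500 | 6% | 12% | 24% |
| 5,000 | 3% | 6% | 12% |

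The spreading rate is a single assumed value. Halving or doubling it halves or doubles each uncapped percentage.

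*Per area or whole trunk.* If chest and back count as two areas, the per-area reading doubles the amount. That moves a subject one column to the right, for example from 0.5 g (0.5 × 75 = 37.5 mg dapsone a day) to 1.0 g (75 mg a day). The text supports either reading.

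**Can the planned data recover this?** The compliance question counts missed days and does not ask about amount. The dispensed and returned records could give total use if kept by weight, but the protocol does not say in what unit they are kept. Affected area is not collected, so gel per cm² cannot be derived even if total use is known.

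**The case against.** Much of the treatment is specified: product, strength, frequency, site, skin preparation and technique. The amount is qualified as approximate, and it can be read as per area. The large-area text is rationale and questionnaire wording, so the tension is between an instruction and its background and not between two dosing figures. A subject with a small affected area can meet both parts of the sentence, as the first row of the table shows for 0.5 g. All of this stands, and it limits the point to what the amount refers to and how it relates to area.

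It can also be argued that Section 5.2.6 already captures use, and that Section 8.2 promises descriptive statistics for all continuous variables collected. This stands in part. The records could be used, but they are described as inventory records, with no unit and no named summary. They would not show which skin was covered.

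A reader might infer three stronger things that the documents do not support:

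- **That the supply contradicts the instruction.** Section 5.2.3 says the gel "is supplied in 90 gram pump" and the schedule shows dispensing at three visits. The number of pumps per visit is not stated, and a surplus in a commercial pack does not contradict an application rule.
- **That the centers will treat differently.** Section 3 says "This is a three-center, open-label pilot study", and all three centers share the same text. Visit 1 instruction could differ, but nothing shows that it will.
- **That treatment is undefined or the results uninterpretable.** The pilot still estimates response under the instruction as given. What it loses is the ability to explain a poor result or to describe exposure.

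**Conclusion.** The point holds in a limited form. Section 5.2.3 gives an approximate amount with no link to affected area or to a measurable unit, and leaves open whether it is per area or for the whole trunk. For subjects with extensive disease, the amount and the coverage requirement may not both be met. Gel per unit area or total daily exposure may therefore vary between subjects, and no planned summary would describe that variation.

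The proportionality between area and exposure follows from the text. The sizes do not: the 20-fold range comes from the assumed areas, and the coverage figures of 3% to 100% (0.25 to 0.5 g) also need the assumed pea weight and spreading rate. They show that the effect could be anywhere from nil to large. They do not estimate what will happen in these 30 subjects. Sample size and significance level are unaffected. The matter should be settled before first dispensing, because ambiguity about what was applied cannot be repaired at analysis.

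**What to change.** Before first dispensing, the sponsor and investigators should:

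1. Reconcile the amount and the coverage requirement in Section 5.2.3 with each other, and with Section 1.1 and the Supplement II questionnaire. The result should be one instruction that a subject with both chest and back acne can follow, stating whether the amount is per area or for the whole trunk. Which amount applies is for them to decide; none is proposed here.
2. Use that same wording for the Visit 1 instruction at all three centers.
3. State the unit in which the Section 5.2.6 records are kept, and add to Section 8.2 a per-subject summary of amount used.

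The cost is a short change to the protocol and the subject instructions, plus one added summary. If use is to be expressed in grams, pumps would need weighing when dispensed and returned. No new visit is needed, since the assessment schedule already shows collection at the follow-up visits. Supply may need re-estimating once the instruction is settled. Amount used would describe total exposure but not coverage. Gel per unit area would also need affected area to be recorded at baseline, which is an optional addition.

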5.2.4 Treatment Assignment

The study medication will be administered only to eligible subjects as defined by the Study Protocol. All subjects who have signed an ICF will receive a 2-digit subject number, starting at 01. This subject number will be used to identify the subject throughout the study. Subjects withdrawn from the study will retain their subject number. New subjects will be allotted a new subject number.

5.2.5 Blinding, Packaging, and Labeling

Commercially available and labeled medication will be used. Medication will be dispensed in an open-label fashion.

5.2.6 Supplies and Accountability

The Investigator or pharmacist will inventory and acknowledge receipt of all shipments of study medication. All study medication must be kept in a locked area with access restricted to designated study personnel. The study medication must be stored in accordance with the instructions provided with the shipment. The Investigator or pharmacist will also keep accurate records of the quantities of study medication dispensed and returned by each subject.

5.2.7 Treatment Compliance

Subject compliance to study treatment regimen will be assessed at each visit; study personnel will ask each subject whether they missed any applications of study medication since the previous visit.

5.3 Concomitant Medication/Treatment

Please see Supplement I for a listing of prohibited medications. Necessary therapies that will not interfere with the response to treatment may be provided at the discretion of the Investigator. The use of any concurrent medication, prescription or over-the-counter drug, is to be recorded in the CRF along with the reason the medication was taken.

ACZ1601 (01JUN2016) Page 8 of 14

6 STUDY ASSESSMENTS

6.1 Primary Endpoint

The primary endpoint of this study is the percent of patients who achieve a two grade improvement and clear or almost clear on IGA scale for truncal acne.

6.1.1 Acne IGA

ESTREL VIOLETTE

The Investigator will evaluate global acne severity using the following Investigator Global Assessment scale:

Score	Description
0 = Clear Skin	Clear Skin; no inflammatory or non-inflammatory lesions
1 = Almost Clear	Almost clear; rare non-inflammatory lesions with no more than one small inflammatory lesion
2 = Mild Severity	Mild severity; greater than Grade 1; some non-inflammatory lesions with no more than a few inflammatory lesions (papules/pustales/cnly; no nodular lesions)
3 = Moderate Severity	Moderate severity; greater than Grade 2; some to many non-inflammatory lesions and may have some inflammatory lesions, but no more than one small nodular lesion
4 = Severe	Severe; greater than Grade 3; some to many non-inflammatory and inflammatory lesions, but no more than a few nodular lesions
5 = Very Severe	Very Severe; greater than Grade 4; many non-inflammatory and/or inflammatory lesions with some or many nodular lesions

